3.1 EVALUATION OF ELIGIBILITY

All patients admitted to the participating centers will be evaluated consecutively by the referent investigators. All patients that meet the above-described criteria will be included in the registry.

3.2 DATA COLLECTION

No additional procedures are required to the participating centers. Data usually collected in the center and necessary for the analysis will be collected by the referent investigator. Considering that ICDs record the principal events of the whole life of the device, patients with an ES previous to the creation of this registry will be included retrospectively providing that:

- 1) clinical data from the participating center are complete and accurate and allow to check inclusion and exclusion criteria
- 2) follow-up is available
- 3) ICD has not been replaced, leading to the loss of original data
- 4) ECG and echocardiography done in routine practice are available in case of necessity
- 5) subject agrees to subscribe the informed consent during the next routine visit in the recruiting center

All data will be used with scientific research purposes only. Data will be saved on a dedicated website⁷ in agreement with current regulations on the treatment of personal data. Electronic cards of data collection transmitted to the study responsible will be identified by an alphanumeric code. The list of matches between subjects' data and these codes will be created and kept by local investigators or delegates. The data manager is the study responsible.

For the type of data requested, see Case Report Form (attachment #3)

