2. AIM OF THE STUDY

The aim of the ELECTRA registry is twofold:

- a) To create an international registry on clinical features, optimal therapy, ablation strategy, prognosis and the effect of ICD programming on patients with ES.
- b) To use the data derived from the registry for a prospective, observational study on mortality and rehospitalization rate in patients with ES.

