3. REGISTRY DESIGN

The creation of the present registry is aimed at gathering information on a wide cohort of patients affected by ES. All patients will be enrolled for a minimum of three years from the protocol approval. There is no pre-specified date for the end of enrollment, which will be decided by the study responsible according to the enrollment rate.

A minimum of 500 patients will be included in the present registry. The exploratory nature intrinsic to the registry characteristics does not allow a sample size calculation by statistical means. However, the sample presented is based on the estimated enrolment rates of the participating centers during a 3-year enrolment period. Moreover, the sample size is large enough to postulate specific subgroup analyses.

REGISTRY INCLUSION CRITERIA:

- Diagnosis of ES (documentation of 3 or more episodes of sustained ventricular arrhythmia within 24h or documentation of sustained ventricular tachycardia lasted at least 12h). In order to fulfill this criterion, a patient with a previous episode of ES could also be enrolled during routine screening.
- Age ≥ 18
- Written informed consent

REGISTRY EXCLUSION CRITERIA:

- patient without ICD
- Confirmed or suspected use of drugs or narcotics with known direct pro-arrhythmic effect
- Inability to express an informed consent for the study

At enrollment, each patient will be informed on the aim and the design of the study, and the investigations needed. All patients that meet the inclusion criteria will be included in the study (attachment #1). All recruited patients will receive the informative form (attachment #1) and the informative letter to their general practitioner (attachment #2).

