4. OBSERVATIONAL STUDY DESIGN

Multicenter, observational, prospective clinical study. Data from the first 500 patients enrolled in the registry will be used for the present analysis. Please see point #3 of the present protocol for information regarding registry enrollment criteria and data collection.

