4.1 PRIMARY ENDPOINT

- All-cause mortality 3 years after the ES

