4.4 STATISTICAL ANALYSIS

The primary endpoint will be estimated annually and it will be expressed as absolute and relative numbers. Survival curves free from study endpoint, eventually divided into subgroups according to variables of interest such as gender, age, underlying heart disease, comorbidity and programming mode, will be drawn with Kaplan-Meier method and compared by Log-rank test. Basal and follow-up parameters (clinical, electrocardiographic and echocardiographic) will be compared by χ^2 test or by Fisher test if they are discrete; by T-student test or signed rank test if they are continuous. Every test will be two-tailed and a value of $p>0.05$ will be considered significant.

According to the number of centers involved we expect to recruit at least 500 patients. Considering an annual incidence of the primary endpoint (death from all causes) of 11% according to our experience (Guerra et al. Europace 2015), we expect about 55 events at the first statistical analysis after one year from the start and we expect about 165 events at the end of the follow-up of three years. The statistical analysis will be conducted using the SPSS 21.0 for Windows software (SPSS Inc. Chicago, IL, USA).

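### Patients with a past ES must survive to sign consent, yet 3-year mortality is counted from the ES with no delayed entry, so it is biased downwards by an amount the documents cannot size

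*Combined protocol and SAP*

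**What the plan says.** Two provisions admit patients whose ES lies in the past. The inclusion criteria in section 3 state that "a patient with a previous episode of ES could also be enrolled during routine screening", with no limit on the time since that episode. Section 3.2 adds that "patients with an ES previous to the creation of this registry will be included retrospectively providing that" five conditions hold, among them that the "subject agrees to subscribe the informed consent during the next routine visit in the recruiting center" and that the "ICD has not been replaced, leading to the loss of original data". Written consent is an inclusion criterion and inability to consent an exclusion. No route is given for a patient who died before the visit.

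Section 2 describes the purpose as "To use the data derived from the registry for a prospective, observational study on mortality and rehospitalization rate in patients with ES". Section 4 repeats the prospective label, states that "Data from the first 500 patients enrolled in the registry will be used for the present analysis", and refers back to section 3 for enrolment and data collection. It does not leave retrospective entrants out.

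The primary endpoint in section 4.1 is "All-cause mortality 3 years after the ES". Section 4.4 says that "The primary endpoint will be estimated annually and it will be expressed as absolute and relative numbers", and plans Kaplan-Meier curves with log-rank comparisons between subgroups. It does not say when a patient enters the risk set.

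The case report form (attachment #3) has ES start and end dates and a last follow-up date. Neither it nor attachment #4 lists a consent or enrolment date.

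**The concern.** A patient enrolled some time after the ES has, by the enrolment rule, already survived that interval. Patients with the same history who died in it never reach the registry. If the clock starts at the ES and everyone is treated as at risk from then, the survivors' event-free time enters the denominator and the matching deaths are absent from the numerator. A patient who consents 3 or more years after the ES cannot contribute a 3-year death at all, yet still counts among the 500.

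The primary estimate is at stake, and the error runs in the falsely reassuring direction. More patients with the same retrospective share and lag do not reduce it. Subgroup log-rank tests are exposed too: groups with identical hazards can appear to differ only because one holds more retrospective patients. Without an entry date in the analysis data, the bias can be neither measured nor corrected.

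**Working it through.** **Inputs.** From section 4.4: 500 patients, 11% annual mortality, about 55 deaths at one year and 165 at three. From section 4.1: time zero at the ES and a 3-year horizon. Retrospective share *f* and ES-to-consent lag *u*: not in the documents, so assumed below.

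**The plan's own figures.** 500 × 0.11 = 55 and 500 × 0.11 × 3 = 165, so both reproduce on a linear scale; 165/500 = 33%. Compounded, 1 − 0.89³ = 29.5%, or 147.5 deaths. I use 29.5% as the main baseline and 33% as a second.

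**Direction.** Let S(t) be survival from the ES. A patient who must survive to *u* has an observable 3-year risk of 1 − S(3)/S(u), which is below 1 − S(3) whenever any deaths occur before *u*. The same holds within one data set. Ignoring entry times can only enlarge the risk set at each death, so Kaplan-Meier mortality without delayed entry can never exceed the delayed-entry estimate.

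**Size under assumed shares and lags.** With a constant hazard h = −ln(0.89) = 0.1165, the observable risk is 1 − exp(−h(3 − u)):

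- u = 0.5 years: 25.3%
- u uniform on 0–1 year: mean 25.2%
- u uniform on 0–3 years: mean 15.6%

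The pooled figure is (1 − f) × 29.5 + f × observable risk. For the 33% baseline, h = −ln(0.67)/3 = 0.1335.

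| Assumed share, lag | Calculation | Counted (true 29.5%) | Bias, points | Counted (true 33%) | Bias, points |
|---|---|---|---|---|---|
| 10%, 6 months | 0.9 × 29.5 + 0.1 × 25.3 | 29.1% | 0.4 | 32.5% | 0.5 |
| 25%, 0–1 year | 0.75 × 29.5 + 0.25 × 25.2 | 28.4% | 1.1 | 31.8% | 1.2 |
| 50%, 0–3 years | 0.5 × 29.5 + 0.5 × 15.6 | 22.6% | 6.9 | 25.3% | 7.7 |
| 75%, 0–3 years | 0.25 × 29.5 + 0.75 × 15.6 | 19.1% | 10.4 | 21.4% | 11.6 |

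Biases are taken from unrounded values. Fixed lags tell the same story: 25% with a 1-year lag gives 27.3% (2.2 points), and 50% with a 2-year lag gives 20.2% (9.3 points).

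**Against sampling error.** The 95% half-width is 1.96 × √(0.295 × 0.705/500) = 4.0 points. The first two scenarios lie well inside it, the last two far outside.

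**Subgroups.** Two groups with the same true hazard, 25% and 50% retrospective, would show 28.4% against 27.4% (lags 0–1 year), or 26.0% against 22.6% (lags 0–3 years).

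**Does delayed entry repair it?** I used a simulation with n = 500, constant hazard, lag independent of survival and 4,000 runs per scenario:

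| Share, lag | Without delayed entry | With delayed entry | Standard error with delayed entry, points |
|---|---|---|---|
| 25%, 0–1 year | 28.4% | 29.5% | 2.1 |
| 50%, 0–3 years | 22.5% | 29.5% | 2.3 |
| 75%, 0–3 years | 19.1% | 29.5% | 2.7 |

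If all 500 were followed from the ES, the standard error would be 2.0 points.

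**The case against.** The best counter-argument is that the problem may be small or unintended. Section 3.1 has admitted patients evaluated consecutively, section 3 bases the sample on enrolment rates over three years, and section 4.4 times its first analysis from the start of the study. Together with the prospective label, this suggests mostly new cases. The 50% and 75% shares and the 3-year ceiling on the lag have no support in the text, and the milder scenarios move the estimate by about one point or less. This stands as a caution about size: the table is a set of scenarios and bounds nothing in either direction. It does not remove the problem, because no provision excludes retrospective patients and section 4 refers back to the rules that admit them.

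The downward direction relative to the truth also assumes that, given survival to consent, time of entry is unrelated to later risk. If sicker survivors attend routine visits more often, part of the bias could be offset. That is fair, and the conditions on available follow-up and an unreplaced ICD in section 3.2 may strain the assumption. The comparison on the same data, with and without entry times, does not depend on it.

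Patients enrolled at the index ES are not a perfect reference either, since those unable to consent in the acute phase are missed. This stands too, and delayed entry does not repair it.

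Finally, restricting the analysis to storms after the registry's start would be simpler. It would not be enough, because the inclusion criteria also admit a past ES found later at routine screening.

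**Conclusion.** The concern holds. Followed as written, the plan gives a 3-year mortality estimate that is too low whenever the first 500 include patients enrolled after their ES. The omission and the survival-to-consent rule are plain in the text. The direction follows from them, provided entry time is otherwise unrelated to prognosis.

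The size is open. The scenarios run from 0.4 to 10.4 points on the compounded baseline and from 0.5 to 11.6 on the plan's linear one, under assumed shares and lags and a constant hazard. If deaths cluster soon after the ES, the bias is larger for the same lag. Calling the exercise exploratory does not excuse it, because the plan names a primary endpoint, an expected event count and formal subgroup comparisons.

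**What to change.** 1. State which patients form the mortality analysis set and how the prospective label fits with section 3.2. Either describe the study as combined retrospective and prospective, or exclude patients not enrolled at their index ES from the mortality analysis.
2. Add the consent (enrolment) date to the case report form and attachment #4. Local consent records may already hold it.
3. If retrospective patients stay, specify in section 4.4 that time zero is the ES and that patients enter the risk set at consent, for Kaplan-Meier, log-rank and any regression added later. Confirm that the planned software accepts entry times, or name one that does.
4. Do not report the primary endpoint only as crude counts over all 500.
5. State the assumption that entry time is independent of survival, with the caveat about the section 3.2 conditions. Report patients enrolled at the index ES separately as a sensitivity analysis, noting that those unable to consent are still missing.

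The cost is one date field, a few sentences in section 4.4 and possibly a software change. Fewer patients are at risk soon after the ES, so intervals widen: the standard error rises from 2.0 points to 2.1–2.7 in the scenarios above. Excluding retrospective patients avoids the method change, but leaves fewer patients or takes longer to reach 500.

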3.3 DATA REPORT

Collected data will be processed, analysed and reported according the Strengthening the Reporting of Observational Studies in Epidemiology (STROBE) Initiative international guidelines.⁸ A descriptive analysis will be performed yearly and at the end of enrolment. This will include:

- The prevalence of cardiovascular risk factors (arterial hypertension, diabetes mellitus, prior stroke or TIA, atrial fibrillation, peripheral vascular disease) in the studied population.
- The acute and chronic management of ES, regarding pharmacological and non-pharmacological treatment.
- Centrality and dispersion measures regarding laboratory, echocolorDoppler and electrophysiological parameters.
- Centrality and dispersion measures regarding ES inherent variables, such as total number of arrhythmias, cycle length and ICD programming.

⁷ <http://clincardio.univpm.it/eulogin.php>

⁸ on Elm E, Altman DG, Egger M, et al. The Strengthening the Reporting of Observational Studies in Epidemiology (STROBE) Statement: Guidelines for reporting observational studies. PLoS Med 2007. 4(10): e296.

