Attachment #3- Case report form

 
Università Politecnica delle Marche - Clinica di Cardiologia Case Report Forms ELECTRA

Fill in following fields and "Enter"

0.1 - General Data
 
Last name  - First name  - Sex  - Birth date  Height (m)  - Weight (kg)  - NYHA 

0.2 - Risk factors and comorbidities
 
Hypertension  - Diabetes mellitus  - Previous Stroke or TIA  - Atrial Fibrillation  Previous episode of documented myocardial ischemia  - Peripheral artery disease 

0.3 - Chronic medical therapy (pre-storm)
 
Amiodarone  - Beta-blockers  - Ranolazine  Antiarrhythmic drugs class 1A  - Antiarrhythmic drugs class 1B  - Antiarrhythmic drugs class 1C  - Sotalol  - Digoxin 

0.4 - Laboratory exam
 
Haemoglobin (g/dl)  - Hematocrit (%)  - Creatinine (mg/dl)  - BNP (ng/dl)  - Kaliemia (mEq/l)  - Magnesemia (mEq/l) 

0.5 - Echocardiography (acute phase)
 
Ejection fraction (%)  - End-diastole interventricular septum (mm)  - End-sistole interventricular septum (mm)  Left ventricular diastolic diameter  - Left ventricular systolic diameter  - End-diastole posterior wall (mm)  - End-sistole posterior wall (mm) 

1.1 - ICD data
 
ICD type  - Implantation date  - Prevention  - Cardiomyopathy  ICD Brand  - ICD Model 

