
1.2 - Detection windows
 
VT detection rate  - VT if >24beats/12s  - ATP on VT  - Shock on VT  VT-1 detection rate (if present)  - VT-1 if >24beats/12s  - ATP on VT-1  - Shock on VT-1  VF detection rate  - VF if >24beats/12s  - ATP during charge 

2.1 - Electrical Storm
 
Electrical Storm geographical location  Electrical Storm start date  - Electrical Storm end date  - Electrical Storm beginning hour  Acute Coronary Syndrome as triggering ES event  - Acute Coronary Syndrome therapy  - ES triggering arrhythmias  Triggering arrhythmias cycle length  - Number of ATP delivered  - Number of shocks delivered  - Hospitalization length (days) 

2.2 - Previous arrhythmic events
 
Previous ES  - Previous VT/VF  - Previous VT ablation  - Previous inappropriate ICD therapies 

2.3 - ES medical management
 
Amiodarone  - Lidocaine  - Beta-blockers  - Sotalol  - Procainamide  Magnesium Sulfate  - Sedation  - Ablation  - CRT upgrade  - Pacing Overdrive  - Heart Transplant 

3.0 - ES ablation
 
Ablation date  - Ablation success  - Ablation number of attempts  - Ablation type  - Ventricular mapping  Endocardial approach  - Epicardial approach  - Electromechanical mapping  - Non contact mapping  - Irrigated tip catheters  Fluoroscopy time (min)  - Total procedure time (min) 

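### Section 3.3 promises a report on chronic drug management of ES, but no visible field records maintenance drugs after the storm

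*Combined protocol and SAP*

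**What the plan says.** Section 3.3 (Data report) lists what will be described each year and at the end of enrolment. One item is "The acute and chronic management of ES, regarding pharmacological and non-pharmacological treatment". Section 2 sets the wider aim: "To create an international registry on clinical features, optimal therapy, ablation strategy, prognosis and the effect of ICD programming on patients with ES".

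Section 3.2 says where the dataset is defined: "For the type of data requested, see Case Report Form (attachment #3". In Attachment #3, chronic drugs appear in one block, headed "0.3 - Chronic medical therapy (pre-storm". Treatment of the storm itself is in "2.3 - ES medical management", with procedural detail in "3.0 - ES ablation". What is collected afterwards is set by CRF block 4.0, Attachment #4 and Section 4.3. The last of these asks centers for new admissions with their cause, and for vital status every six months.

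**The concern.** Management of ES has to mean what is done because of the storm. Its chronic drug component is the regimen on which the patient leaves hospital and is then maintained. The form asks about chronic drugs at the one time point that precedes the event being managed.

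Two things are at stake. First, an explicit report item has no data source for drugs. If the pre-storm block were used to fill it, the table would show the therapy on which the storm occurred, under a heading that says otherwise. Second, if anyone later relates long-term drug therapy to mortality or recurrence, the only exposures available are pre-storm and storm-time. These are out of date for patients whose drugs changed because of the storm, and those are the patients that a registry concerned with therapy most needs to describe. Analysis cannot recover a variable that was never collected.

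**Working it through.** The plan gives no figure on this point and no sample-size or power arithmetic enters. The check is a count of every treatment field on the forms, set against the promised report item.

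| Place | Fields | Treatment content |
|---|---|---|
| CRF 0.3 | 8 | Amiodarone, beta-blockers, ranolazine, class 1A, class 1B, class 1C, sotalol, digoxin; all pre-storm |
| CRF 2.3 | 11 | 7 drug or sedation items (amiodarone, lidocaine, beta-blockers, sotalol, procainamide, magnesium sulfate, sedation) and 4 non-drug items (ablation, CRT upgrade, overdrive pacing, heart transplant) |
| CRF 3.0 | – | Ablation date, success, attempts and technique |
| CRF 4.0 | 8 | 0 |
| Attachment #4 | 8 | 0 |
| Section 4.3 updates | – | Admissions and vital status; no therapy |

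**Step 1: the four parts of the promise.** Acute drug treatment is covered by the 7 drug or sedation items in 2.3. Acute non-drug treatment is covered by the 4 other items and block 3.0. Longer-term non-drug treatment is partly covered, through ablation, CRT upgrade and transplant. For longer-term drug treatment after the storm, the visible fields are 0 in block 4.0 + 0 in Attachment #4 + 0 in the Section 4.3 updates = 0.

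**Step 2: can block 2.3 stand in?** It shows no date, discharge or continuation field. The options behind its Select fields are not reproduced, so a choice such as 'continued' cannot be ruled out. Suppose it exists, and compare the two drug lists. Of the eight chronic items in 0.3:

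- three appear in 2.3 under the same name (amiodarone, beta-blockers, sotalol);
- two (class 1A and class 1B) are not named there as classes, although 2.3 lists the individual drugs procainamide and lidocaine;
- three have no entry at all (ranolazine, class 1C, digoxin).

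So 3 + 2 + 3 = 8, and even on the most generous assumption a newly started drug from the last group has nowhere to go. Nor does any visible field record that a pre-storm drug was stopped.

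**Step 3: what one patient's record shows.** Take a patient not on amiodarone before the storm, given it for the storm and then kept on it. Block 0.3 correctly reads no, and block 2.3 records its use. What is lost is whether it was continued.

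**The case against.** The best case for the plan has four parts.

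- *The Select menus are unseen.* This is a fair limit on certainty about block 2.3. It does not close the gap, because three of the eight chronic drug items have no entry there.
- *Section 3.2 speaks generally of data that centers usually collect and the analysis needs.* The same section sends the reader to the CRF for the type of data, and an item without a field does not reach the database in usable form.
- *Chronic management could mean background therapy before the storm.* Section 3.3 ties the word management to ES, and drugs taken before the storm are not management of it.
- *Only part of one descriptive item is lost.* This stands. All-cause mortality and all-cause hospitalization do not need a drug field.

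A reader might also infer more than the documents support:

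- *That post-storm treatment is unknown for every patient.* It is not: ablation, CRT upgrade and transplant are recorded. The gap is in drugs.
- *That a planned comparison of therapy with mortality will be wrong.* No such analysis is specified. Section 2 names therapy and prognosis side by side as topics. Section 4.4 gives gender, age, underlying heart disease, comorbidity and programming mode as examples of subgroup variables. The list is open, so the consequence for outcome analyses is conditional.
- *That a given number of patients would be misclassified.* The documents give no figure for how many have drugs started, stopped or switched after a storm, so no count can be defended.
- *That the pre-storm block will be reported as chronic management.* No section says so; it is a risk only because nothing else is available.

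**Conclusion.** The point holds for drug therapy. On the visible forms, the pharmacological half of the chronic-management item in Section 3.3 cannot be delivered: there are eight chronic drug fields before the storm and none after it. Any optional analysis of long-term drugs against outcome would have to use pre-storm or storm-time exposure.

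The conclusion assumes that Attachments #3 and #4 are the full dataset, as Section 3.2 indicates for the former. It also allows that unseen Select options could narrow the gap for drugs listed in block 2.3, but could not close it. This is a change that should be made because it is cheap and restores a stated deliverable. It does not threaten the study's main result.

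**What to change.** Add one block to Attachment #3 that repeats the eight drug fields of CRF 0.3 as chronic medical therapy at discharge after ES, or at the first visit after the storm if the patient was not admitted. Include an option for death before discharge, so that an empty block is not read as no therapy. Enter the date to which the block refers; the form now has storm dates and length of stay but no discharge date. Report chronic management in Section 3.3 from this block, with the change from pre-storm shown.

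A single record at discharge misses later starts, stops and switches. If feasible, add the same eight items to the six-monthly update in Section 4.3 and to Attachment #4.

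Therapy at discharge exists only for those who reach discharge, whereas the endpoint in Section 4.1 is counted from the storm. If the block is ever related to mortality or recurrence, start follow-up at discharge (a landmark) among survivors. For patients not admitted, use the date of the first visit in the same way.

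If the fields cannot be added, limit the Section 3.3 item to pre-storm and storm drug treatment, which costs only a wording change.

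Cost of the main fix: a small change to the form and website, eight Select fields and a date per patient, and a one-time back-fill from existing records for patients already entered. Section 3.2 already requires complete and accurate clinical data for retrospective patients, and no procedure is added.
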